6.1. REFERENCE START DATE AND STUDY DAY

Study Day will be calculated from the reference start date and will be used to show start/ stop day of assessments and events.

Reference start date is defined as the day of the first dose of study medication, (Day 1 is the day of the first dose of study medication) and will appear in every listing where an assessment date or event date appears.

- If the date of the event is on or after the reference date, then:

Study Day = (date of event – reference date) + 1.

- If the date of the event is prior to the reference date, then:

Study Day = (date of event – reference date).

Document: Statistical Analysis Plan

Author: [name]

Version Number: 1.1

Version Date: 18Jan2023

Template No.: CS_TP_BS016 Revision 5

Reference: CS_WI_BS005

Effective Date: 01Apr2018

In the situation where the event date is partial or missing, the date will be imputed based on the imputation rules specified in section 11. The original value will be listed in the listings. The study day and any corresponding durations for this record will be calculated based on the imputed date.

6.2. BASELINE

For stage 1: Unless otherwise specified, baseline is defined as the last non-missing measurement taken prior to the first treatment date (including unscheduled assessments) in stage 1. In the case where the last non-missing measurement and the reference start date coincide, and no time collected, that measurement will be considered pre-dose, except that the protocol specifies the measurement is post-dose.

For subject randomized but not treated, baseline is defined as the last non-missing measurement on or before randomization date.

For subjects entered into stage 2 sub-study 1: the baseline will be the same as in stage 1.

For subjects entered into stage 2 sub-study 2: the baseline is defined as the last non-missing measurement taken prior to the first treatment date (including unscheduled assessments) in stage 2 sub-study 2.

For all stages (0.2mg only) analysis, baseline will be the same as in stage 1.

6.3. RETESTS, UNSCHEDULED VISITS

In general, for by-visit summaries, data recorded at the nominal visit will be presented. Unscheduled measurements will not be included in by-visit summaries but will contribute to the minimum, maximum, best or worst case value where required (e.g. shift table).

Unless otherwise specified, in the case there are more than one records in the same visit, the latest available measurement for that visit will be used for by-visit summaries.

Listings will include scheduled, unscheduled, retest data.

Document: Statistical Analysis Plan

Author: [name]

Version Number: 1.1

Version Date: 18Jan2023

Template No.: CS_TP_BS016 Revision 5

Reference: CS_WI_BS005

Effective Date: 01Apr2018

6.4. COMMON CALCULATIONS

For quantitative measurements, change from baseline will be calculated as:

- Change from baseline = Value at Week X – Baseline Value

Percentage change from baseline will be calculated as:

- Percentage change from Baseline = $(\text{Value at Week X} - \text{Baseline Value}) / \text{Baseline Value} \times 100\%$

6.5. SOFTWARE VERSION

All analyses will be conducted using SAS 9.4 or higher version.

7. STATISTICAL CONSIDERATIONS

7.1. MULTICENTER STUDIES

Center pooling will not be carried out for use in analyses for this study.

7.2. MISSING DATA

Missing safety data will be handled as described in separated section (concomitant medication missing data rule in section 11, and adverse event missing data rule in section 15.1).

Missing efficacy data will be handled as described in section 14.1.2 of this analysis plan.

7.3. SUBGROUP ANALYSES

No planned subgroup analyses will be performed for this study.

Document: Statistical Analysis Plan

Author: [name]

Version Number: 1.1

Version Date: 18Jan2023

Template No.: CS_TP_BS016 Revision 5

Reference: CS_WI_BS005

Effective Date: 01Apr2018

7.4. SAMPLE SIZE

Approximately 134 subjects with moderate to severe UC will be randomized in the study. Among them, there are approximately 30 subjects in the CBP-307 0.1 mg once daily group. In protocol version 5.0 or earlier, 195 patients with moderate to severe UC were planned to be randomized at 1:1:1 into any of the following 3 groups: CBP-307 0.1 mg once daily, CBP-307 0.2 mg once daily, placebo. Approximately 65 subjects were planned to be in each group. However, protocol amendment happens during the treatment period. The primary endpoint analysis is based on the comparison between the 0.2 mg CBP-307 group and the placebo group, and protocol version 6.0 keeps only these two groups, and sample size is re-calculated. The 0.1 mg group is not applicable in protocol version 6.0, and there will be no further subjects enrolled in the 0.1 mg group. The nearly 30 subjects already randomized with protocol version 5.0 or earlier are kept and analyzed for exploratory purpose.

The sample size re-calculation is based on the comparison between CBP-307 0.2 mg once daily group and placebo group on the primary efficacy endpoint, namely the change in adapted Mayo score from baseline at week 12 after treatment. Assuming that the difference between the 0.2 mg group and the placebo group of the change from baseline at week 12 after treatment in adapted Mayo score is 1.2, and the common standard deviation is 2.0, a significance level of $\alpha=0.05$ (two-sided), and a dropout rate is 15%, then each group needs to enroll at least 52 subjects (104 subjects in two groups) to provide a power of 80% to detect the difference between the 0.2 mg group and the placebo group on the primary efficacy endpoint. Based on this estimation, the eligible subjects with moderate to severe UC will be randomized at 1:1 into CBP-307 0.2 mg once daily group or placebo group until 52 subjects are enrolled into each group.

8. DISPOSITION AND WITHDRAWALS

Disposition of all screened subjects, Screen failure, screened but not randomized will be

Document: Statistical Analysis Plan

Author: [name]

Version Number: 1.1

Version Date: 18Jan2023

Template No.: CS_TP_BS016 Revision 5

Reference: CS_WI_BS005

Effective Date: 01Apr2018

summarized by count and percentage.

Disposition of all randomized subjects will be tabulated by randomized treatment. The categories will include:

Stage 1:

- All subjects screened
- Screen Failed
- Screen success but not randomized
- All randomized subjects
- Subjects who were randomized but not treated with study medication
- Status of study treatment
 - completed
 - Ongoing
 - Discontinued
- Primary reason for treatment discontinuation
- Entered stage 2

- Study Status
 - Early discontinued in stage 1
 - Stage 1 treatment ongoing
 - Stage 1 post treatment follow-up
 - Completed stage 1 but not entered stage 2
 - Entered stage 2
- Primary reason for study discontinuation

Stage 2:

- Subjects archived clinical response by adapted mayo score (for sub-study 1)/ Subjects not archived clinical response by adapted mayo score (for sub-study 2)

Document: Statistical Analysis Plan

Author: [name]

Version Number: 1.1

Version Date: 18Jan2023

Template No.: CS_TP_BS016 Revision 5

Reference: CS_WI_BS005

Effective Date: 01Apr2018

- All subjects screened
- Status of study treatment
 - Completed
 - Ongoing
 - Discontinued
- Primary reason for treatment discontinuation
- Study Status
 - Early Discontinued in Stage 2
 - Stage 2 Treatment Ongoing
 - Stage 2 Post Treatment Follow-Up
 - Completed
- Primary reason for study discontinuation

Primary reasons for treatment discontinuation, as entered on the eCRF, will be tabulated; the reasons include adverse event, significant protocol deviation, death, non-compliance problems, lost to follow-up, withdrawal by subject, study terminated by sponsor, pregnancy, lack of efficacy or disease progression, or other. COVID-19 will be presented separately after selected from other reasons in 'Other, Specify' category.

Primary reasons for study discontinuation, as entered on the eCRF, will be tabulated; the reasons include subject didn't meet eligibility criteria(s), adverse event, significant protocol deviation, death, non-compliance problems, lost to follow-up, withdrawal by subject, study terminated by sponsor, pregnancy, lack of efficacy or disease progression, or other. COVID-19 will be presented separately after selected from other reasons in 'Other, Specify' category.

0.2mg only for all stages will present both stage 1 and stage 2 disposition.

Completed or discontinued from study, duration of study, and the reason for study withdrawal will be listed for each safety subject in the listings.

Major protocol deviation leading to subject being excluded from FAS in PPS and summary of all analysis sets will be presented for the safety set and be listed in the listings. Listing of

Document: Statistical Analysis Plan

Author: [name]

Version Number: 1.1

Version Date: 18Jan2023

Template No.: CS_TP_BS016 Revision 5

Reference: CS_WI_BS005

Effective Date: 01Apr2018

inclusion/exclusion criteria responses by subject will also be provided.

9. DEMOGRAPHIC AND OTHER BASELINE CHARACTERISTICS

Demographic data and other baseline characteristics will be presented for randomized population. The following demographic and other baseline characteristics will be reported for this study:

- Age (years) - calculated relative to date of consent
- Sex, including childbearing potential for female subjects
- Race
- Ethnicity
- Weight (kg)
- Height (cm)
- BMI (kg/m²)
- Alcohol use
- Drug abuse
- Tobacco use
- If Treatment with a Tumor Necrosis Factor (TNF)- α Antagonist Failed?
- Ulcerative colitis history
 - Years since UC diagnosis (years)
 - Stool frequency (times/day)
 - Rectal bleeding
 - Endoscopy score - investigator
 - Endoscopy score - central
 - Physician's global assessment
 - Location and extent of subject's UC
- Family history of colon cancer

Document: Statistical Analysis Plan

Author: [name]

Version Number: 1.1

Version Date: 18Jan2023

Template No.: CS_TP_BS016 Revision 5

Reference: CS_WI_BS005

Effective Date: 01Apr2018

- Family history of premature coronary heart disease
- Chest imaging examination results at baseline

BMI (kg/ m²) = weight (kg)/ height (m²)

Age (Years) = (date of informed consent – date of birth+1)/365.25

Years since UC diagnosis = (date of informed consent-date of diagnosis+1)/365.25

10. MEDICAL HISTORY

Medical History/ Ulcerative Colitis Medical History will be presented for the FAS.

Medical history collected at screening will be coded using the Medical Dictionary for Regulatory Activities (MedDRA) V21.1 or higher.

Medical history will be summarized by system organ system (SOC) and preferred term (PT) for each treatment group and overall. The tables will be sorted in descending order by SOC and in decreasing frequency based on the total number of subjects by PT (sorted in alphabetic order in case the frequency coincident) in each SOC. The number and percentage of subjects with any medical history will be summarized for each SOC and PT. The denominator used for calculating the percentages will be the total number of subjects included in each treatment group. For the tables, if a subject report the same PT multiple times, then that PT will be counted only once for that subject. Similarly, if a subject reports multiple conditions within the same SOC, then that SOC will be counted only once for that subject in the tables.

No inferential statistics will be generated.

Medical history will be listed by treatment group, study center and subject number. A by-subject listing of ulcerative colitis medical history will be provided by subject number (in ascending order) and medical history of abnormalities (in chronological order).

Document: Statistical Analysis Plan

Author: [name]

Version Number: 1.1

Version Date: 18Jan2023

Template No.: CS_TP_BS016 Revision 5

Reference: CS_WI_BS005

Effective Date: 01Apr2018

11. MEDICATIONS AND PROCEDURES

Medications will be presented for the FAS and coded using World Health Organization Drug Dictionary Global (Enhanced WHO Herbal Dictionary) 01Sep2018 or higher. Medications will be presented by Preferred name. Procedures recorded will be coded using MedDRA Version 21.1 or higher. All procedures will be presented by SOC and PT.

All medications and procedures will be presented in a listing.

The following rule is used for handling of partial dates for medications, in the case where it is not possible to define a medication as prior, concomitant, or post treatment, the medication will be classified by the worst case; i.e. concomitant. For concomitant medications, incomplete (i.e., partial missing) start date and/or stop date will be imputed. When the start date and the stop date are both incomplete for a subject, consider imputing the start date first.

Missing day and month

- If the year of the incomplete start date is the same as the year of the date of the treatment start date, then the day and month of the treatment start date will be assigned to the missing fields.
- If the year of the incomplete start date is before the year of the date of the treatment start date, then December 31 will be assigned to the missing fields.
- If the year of the incomplete start date is after the year of the date of the treatment start date, then January 1 will be assigned to the missing fields.

Missing month only

- The day will be treated as missing and both month and day will be replaced according to the above procedure.

Missing day only

- If the month and year of the incomplete start date are the same as the month and year of

Document: Statistical Analysis Plan

Author: [name]

Version Number: 1.1

Version Date: 18Jan2023

Template No.: CS_TP_BS016 Revision 5

Reference: CS_WI_BS005

Effective Date: 01Apr2018

the treatment start date, then the treatment start date will be assigned to the missing day.

- If either the year is before the year of the treatment start date or if both years are the same, but the month is before the month of the treatment start date, then the last day of the month will be assigned to the missing day.
- If either the year is after the year of the date of the treatment start date or if both years are the same, but the month is after the month of the treatment start date, then the first day of the month will be assigned to the missing day.

If the stop date is not missing and the start date is after the stop date after missing value calculation, the stop date will be used for the start date.

Incomplete Stop Date

Missing day and month

- If the year of the incomplete stop date is the same as the last treatment date, then the day and month of the last treatment date will be assigned to the missing fields.
- If the year of the incomplete stop date is before the year of the last treatment date, then December 31 will be assigned to the missing fields.
- If the year of the incomplete stop date is after the year of the last treatment date, then January 1 will be assigned to the missing fields.

Missing month only

- The day will be treated as missing and both month and day will be replaced according to the above procedure.

Missing day only

- If the month and year of the incomplete stop date are the same as the month and year of the last treatment date, then the day of the last treatment date will be assigned to the missing day.

Document: Statistical Analysis Plan

Author: [name]

Version Number: 1.1

Version Date: 18Jan2023

Template No.: CS_TP_BS016 Revision 5

Reference: CS_WI_BS005

Effective Date: 01Apr2018

- If either the year is before the year of the last treatment date or if both years are the same, but the month is before the month of the last treatment date, then the last day of the month will be assigned to the missing day.
- If either the year is after the year of the date of the last treatment date or if both years are the same, but the month is after the month of the last treatment date, then the first day of the month will be assigned to the missing day.

If the start date is not missing and the stop date is before the start date after missing value calculation, the start date will be used for the stop date.

‘Prior’ medications are medications which started and stopped prior to the first dose of study medication.

‘Concomitant’ medications are medications which:

- started prior to, on or after the first dose of study medication and started no later than end of study medication,
- AND ended on or after the date of first dose of study medication or were ongoing at the end of the study.

12. STUDY MEDICATION EXPOSURE

Exposure to study medication in days will be presented for the FAS.

The extent of exposure to study medication will be presented for the following summaries by treatment group and overall:

- Duration of exposure (days) during regular treatment period:
Duration of exposure (days) during regular treatment = date of last dose during the regular treatment period – date of first dose during the regular treatment period +1;
- Actual duration of exposure (days) is defined as the total number of days on the study drug during the treatment phase (excluding the periods of dose break or dose interruptions).
- Planned cumulative dose (mg) during the regular treatment period:

Document: Statistical Analysis Plan

Author: [name]

Version Number: 1.1

Version Date: 18Jan2023

Template No.: CS_TP_BS016 Revision 5

Reference: CS_WI_BS005

Effective Date: 01Apr2018

Planned cumulative dose (mg) is defined as the sum of the total planned dosage that the subject should take during the regular treatment period. (subjects are planned to take drug after coming to site).

Stage 1 and Stage 2 Sub-study 1

Treatment Group	Target Visit Day	Planned Daily Dose (mg)	Target Duration	Target Dose Level in the Target Visit (mg)	Planned Cumulative Dose (mg)
0.2 mg QD	W1D5	0.05	4	0.2	0.2
	W2D8	0.1	3	0.3	0.5
	W4D28	0.2	21	4.2	4.7
	W8D56	0.2	28	5.6	10.3
	W12D84	0.2	28	5.6	15.9
	W18D126	0.2	42	8.4	24.3
	W24D168	0.2	42	8.4	32.7
	W32D224	0.2	56	11.2	43.9
	W40D280	0.2	56	11.2	55.1
	W48D336	0.2	56	11.2	66.3
0.1 mg QD (for protocol version 5.0 or earlier)	W1D5	0.05	4	0.2	0.2
	W2D8	0.1	3	0.3	0.5
	W4D28	0.1	21	2.1	2.6
	W8D56	0.1	28	2.8	5.4
	W12D84	0.1	28	2.8	8.2
	W18D126	0.1	42	4.2	12.4
	W24D168	0.1	42	4.2	16.6
	W32D224	0.1	56	5.6	22.2
	W40D280	0.1	56	5.6	27.8
	W48D336	0.1	56	5.6	33.4
Placebo	W1D5	1 tablet	4	4 tablets	4 tablets
	W2D8	2 tablets	3	6 tablets	10 tablets
	W4D28	2 tablets	21	42 tablets	52 tablets
	W8D56	2 tablets	28	56 tablets	108 tablets
	W12D84	2 tablets	28	56 tablets	164 tablets
	W18D126	2 tablets	42	84 tablets	248 tablets
	W24D168	2 tablets	42	84 tablets	332 tablets
	W32D224	2 tablets	56	112 tablets	444 tablets

Document: Statistical Analysis Plan

Author: [name]

Version Number: 1.1

Version Date: 18Jan2023

Template No.: CS_TP_BS016 Revision 5

Reference: CS_WI_BS005

Effective Date: 01Apr2018

	W40D280	2 tablets	56	112 tablets	556 tablets
	W48D336	2 tablets	56	112 tablets	668 tablets

Stage 2 Sub-stage 2

Treatment Group	Target Visit Day	Mappe d Visit Day	Planned Daily Dose (mg)	Target Duration	Target Dose Level in the Target Visit (mg)	Planned Cumulative Dose (mg)
0.2 mg QD	W13D5	5	0.05	4	0.2	0.2
	W14D8	8	0.1	3	0.3	0.5
	W16D112	28	0.2	21	4.2	4.7
	W24D168	84	0.2	56	11.2	15.9
	W32D224	140	0.2	56	11.2	27.1
	W40D280	196	0.2	56	11.2	38.3
	W48D336	252	0.2	56	11.2	49.5

- Actual cumulative dose (mg) during the regular treatment period:

Actual cumulative dose (mg) is defined as the sum of the total dosage that the subject taken during the regular treatment period.

- Planned dose Intensity (mg/day) during the regular treatment period:

Planned dose intensity (mg/day) during the regular treatment period = planned cumulative dose (mg) during the regular treatment period/duration of exposure (days) during regular treatment period*100.

- Dose intensity (mg/day) during the regular treatment period:

Dose intensity (mg/day) during the regular treatment period = actual cumulative dose (mg) during the regular treatment period/duration of exposure (days) during regular treatment*100.

- Relative dose intensity (mg/day) during the regular treatment period:

Relative dose intensity (mg/day) during the regular treatment period=dose intensity during the regular treatment period/planned dose intensity during the regular treatment period*100.

Duration of exposure during the regular treatment period, total duration of exposure, planned cumulative dose during the regular treatment period, planned cumulative dose, actual cumulative

Document: Statistical Analysis Plan

Author: [name]

Version Number: 1.1

Version Date: 18Jan2023

Template No.: CS_TP_BS016 Revision 5

Reference: CS_WI_BS005

Effective Date: 01Apr2018

dose during the regular treatment period, total actual cumulative dose, planned dose intensity during the regular treatment period, dose intensity during the regular treatment period, relative dose intensity (mg/day) during the regular treatment period will be summarized using descriptive statistics, i.e., number of subjects (n), mean, median, standard deviation (SD), 25th and 75th percentiles (Q1, Q3), minimum and maximum.

In addition, the exposure data for the SS will be included in a listing.

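### The two mg/day dose-intensity formulas in SAP section 12 carry a stray factor of 100, so exposure programmed as written would be reported at 100 times its true value

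*SAP*

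**What the plan says.** SAP section 12 (Study Medication Exposure) defines three linked variables for the regular treatment period.

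- Planned dose intensity, unit mg/day: "planned cumulative dose (mg) during the regular treatment period/duration of exposure (days) during regular treatment period*100".
- Dose intensity, unit mg/day: "actual cumulative dose (mg) during the regular treatment period/duration of exposure (days) during regular treatment*100".
- Relative dose intensity: "dose intensity during the regular treatment period/planned dose intensity during the regular treatment period*100". Its label is "Relative dose intensity (mg/day) during the regular treatment period".

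The inputs are unscaled. Duration of exposure is "date of last dose during the regular treatment period – date of first dose during the regular treatment period +1", a plain count of days. Cumulative dose is a plain sum in mg, and the section tabulates the planned values by visit. The last paragraph of section 12 lists all three variables for descriptive summary, and SAP section 4.2 includes the exposure table in the interim (primary) analysis. SAP section 13 then uses relative dose intensity as the compliance measure, with cut-points at 80% and 120%.

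**The concern.** A dose in mg divided by a duration in days is in mg/day with no further conversion. The factor of 100 turns a ratio into a percentage, so it fits the third formula but not the first two. The mg/day label fits the first two but not the third. The likely explanation is that the percentage factor was carried into the two formulas above and the unit label into the one below.

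At stake are two reported exposure variables that would be wrong by two orders of magnitude. Protocol section 3.5 says the study should help determine the phase III dose. A mean of about 19 mg/day in a 0.2 mg arm would contradict both the assigned dose and the cumulative dose in the same table.

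There is also a programming risk. The stray factors cancel in relative dose intensity only if both formulas keep them or both drop them. If a programmer silently corrected just one, a fully compliant subject would score either 1% or 10,000%, and that variable feeds the 80%/120% per-protocol rule.

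**Working it through.** **Inputs.** Planned daily doses, target durations and planned cumulative doses come from the two tables in SAP section 12. The formulas are those quoted above.

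**Step 1: reproduce the plan's cumulative doses.**

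- 0.2 mg arm to day 84: 4 × 0.05 + 3 × 0.1 + 21 × 0.2 + 28 × 0.2 + 28 × 0.2 = 0.2 + 0.3 + 4.2 + 5.6 + 5.6 = 15.9 mg. This matches the row "W12D84 0.2 28 5.6 15.9". The days sum to 4 + 3 + 21 + 28 + 28 = 84.
- 0.2 mg arm to day 336 (stage 1 plus sub-study 1): 15.9 + 8.4 + 8.4 + 11.2 + 11.2 + 11.2 = 66.3 mg. This matches "W48D336 0.2 56 11.2 66.3".
- Sub-study 2, 252 mapped days: 0.2 + 0.3 + 4.2 + 4 × 11.2 = 49.5 mg, as tabulated.
- The 0.1 mg arm also reproduces: 8.2 mg at day 84 and 33.4 mg at day 336.

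The tabulated numerators are therefore correct, and they are in plain mg.

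**Step 2: apply the formula with and without the factor**, for a subject who takes every planned dose.

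| Arm and period | mg / days | mg/day | As written (× 100) |
|---|---|---|---|
| 0.2 mg, stage 1 | 15.9 / 84 | 0.189 | 18.93 |
| 0.2 mg, stage 1 + sub-study 1 | 66.3 / 336 | 0.197 | 19.73 |
| 0.1 mg, stage 1 | 8.2 / 84 | 0.098 | 9.76 |
| 0.1 mg, stage 1 + sub-study 1 | 33.4 / 336 | 0.099 | 9.94 |
| Sub-study 2 (0.2 mg) | 49.5 / 252 | 0.196 | 19.64 |

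The values without the factor sit just below the target doses, as they should after a one-week titration. The values as written are exactly 100 times larger.

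**Step 3: try the other reading.** If the 100 is taken as part of the denominator, the stage 1 result is 15.9 / (84 × 100) = 0.00189 mg/day, which is 100 times too small. Neither reading gives a correct mg/day value.

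**Step 4: check relative dose intensity.** Take a 0.2 mg subject who took 90% of the planned stage 1 dose.

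- As written: dose intensity = 0.9 × 15.9 / 84 × 100 = 17.04; planned = 18.93; ratio × 100 = 90.
- Without the stray factors: 0.1704 / 0.1893 × 100 = 90.

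The result is the same, so the compliance categories in SAP section 13 and the per-protocol compliance criterion in SAP sections 5.1 and 5.2 do not change.

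**The case against.** The strongest reply concerns weight. Relative dose intensity is the only one of the three variables used downstream, and it is numerically right. Per-protocol membership, the primary and secondary analyses and the safety analyses are untouched. PK/PD is handled under a separate plan, and no stated decision rests on dose intensity in mg/day. Under protocol version 6.0 only 0.2 mg and placebo are randomized, and the 0.1 mg subjects are exploratory, so the dose-finding role is limited.

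It can also be said that the inflation appears only if the formulas are programmed literally. Outputs follow table shells that are not part of these documents. Cumulative dose and duration are summarized next to the intensity rows, so a reader could recompute the true value, and 18.9 mg/day in a 0.2 mg arm would stand out.

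All of this stands as a limit on the consequences. None of it makes the formulas right: no other section rescales the inputs, and the factor appears in both mg/day definitions, so it is not a one-off misprint. Being easy to notice is no reason to leave a wrong definition in an operative analysis plan.

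**Conclusion.** The point holds. Both mg/day formulas in SAP section 12 are wrong as written. They inflate planned and actual dose intensity exactly 100-fold, for example 18.9 instead of 0.189 mg/day for full compliance in the 0.2 mg arm at week 12. Relative dose intensity is computed correctly but carries the wrong unit.

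The illustrations assume that every planned dose is taken and that the titration week counts towards the regular treatment period, as the section 12 tables have it. The factor does not depend on either assumption. With titration excluded, for instance, stage 1 would give 77 × 0.2 / 77 = 0.2 mg/day, reported as 20.

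The severity is low: two descriptive exposure variables are affected and no inference changes.

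**What to change.** In SAP section 12:

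1. Delete the factor of 100 from the planned dose intensity formula and from the dose intensity formula. Change both together.
2. Keep the factor in relative dose intensity and replace its mg/day label with a percent sign. The label occurs three times: in the bullet heading, in the formula and in the closing summary paragraph.

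That is five text edits. It is worth stating a unit for placebo intensity at the same time, because that arm's planned dose is tabulated in tablets and mg/day does not apply to it.

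If exposure outputs have already been programmed or produced, check that the code matches the corrected definitions. The change touches no endpoint, sample size, analysis population or study procedure.
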